Ethics Committee approval (was it ethically approved by the department):

This protocol has been approved by the Ethics Committee at Theodor Bilharz Research Institute.

Study Methods:

Population of study & disease condition:

> 75 patients(ASA I or II) undergoing midline hernia repair under general anesthesia will be recruited and will be randomly allocated using a computer generated randomization table (research randomizer, https://www.randomizer.org). The allocation was kept in brown sealed envelopes.

- > Control group.
- > Field block infilteration group.
- ➤ Ultra sound Guided Rectus sheath block group.

Inclusion criteria:

- 1. Elective midline hernia repair surgery.
- 2. Age: adult patients between 18 60 years old.
- 3. Gender: Both male and female.
- 4. ASA Class: I & II.

Exclusion criteria:

- 1. Refusal of patient.
- 2. Pregnancy and lactation.
- 3. Fever or sepsis.
- 4. Patients ASA III or IV.
- 5. Renal impairment.
- 6. Addicts and drug abusers.

- 7. Patients taking corticosteroids or any cardio active drugs.
- 8. Local infection at site of the injection.
- 9. Allergy to any of the study medications.

Methodology in details:

Anesthesia technique:

✓ Preoperative :

- During the pre-operative period visual analog scale (VAS) for pain assessment from 0 to 10, with 0 meaning no pain and 10 meaning the worst pain imaginable will be explained to patients.
- 30 minute before surgery, IV 20 G cannula will be inserted in each patient forearm to collect 5 ml venous blood as preoperative sample for estimation of the level of cortisol and catecholamine.

✓ Monitoring:

In theatre, a five-lead ECG, non-invasive blood pressure, pulse oximetry, end-tidal carbon dioxide and neuromuscular monitoring (Infinity Kappa, Dräger, Lübeck, Germany). Bi-spectral (BIS) module (Infinity® BISxTM SmartPod®, smoothing rate: 15 or 30 seconds, software revision: VF5) was attached to the patients' forehead for the depth of anaesthesia monitoring using disposable BIS electrodes (BIS Quatro, Aspect Medical Systems, USA) after proper skin preparation, were attached to the patient

✓ Induction and maintenance

- During mask preoxygenation, patients baseline hemodynamic parameters will be recorded regarding blood pressure, heart rate.
- General anesthesia will be standardized for all patients with:

2 μg kg⁻¹ fentanyl and 2 mg kg⁻¹ propofol. Neuromuscular blockade will be achieved with 0.5 mg kg⁻¹ atracurium followed by tracheal intubation.

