Assessment of postoperative pain with each technique.

Secondary outcome parameters (other outcomes to be assessed) :

- Assessment of stress response with each technique through measuring cortisol and catecholamine levels.
- Hemodynamic Parameters regarding blood pressure and heart rate.
- Incidence of nausea and vomiting post operative.

- Modified Aldrete score.
- Time to hospital discharge.

STATISTICAL METHODS:

Sample size calculation was done using the comparison of postoperative pain score between RSB, local infiltration and control groups as it was the primary outcome of our study. As reported in previous publication (6,7) the mean \pm S.D. of postoperative pain score in RSB group was 4.65 ± 2.1 , while in local infiltration group it was 5.45 ± 1.9 and in control group it was 7.1 ± 1.1 . We calculated that a sample size of 23 in each group will be able to detect a one unit difference between the groups with 80% power at $\alpha = 0.05$ level using analysis of variance test (one way ANOVA test) for independent samples. The sample size calculation was done using the G*Power© software (Institut für Experimentelle Psychologie, Heinrich Heine Universität, Düsseldorf, Germany) version 3.1.9.2. To allow for drop-outs, 25 patients in each group were recruited.

The statistical analysis was performed using IBM SPSS® Statistics version 22 (IBM® Corp., Armonk, NY, USA). Numerical data were expressed as mean and standard deviation or median and range as appropriate. The qualitative data were expressed as frequency and percentage. The relation between qualitative variables was examined using either Pearson's Chi-square test or Fisher's exact test.

The quantitative continuous data were tested for normality using the Kolmogorov-Smirnov test and the Shapiro-Wilk test. The comparisons between the three groups were done using either analysis of variance (ANOVA) for normally distributed quantitative variables or Kruskal-Wallis test (non-parametric ANOVA) for none-normally distributed data then post-hoc test" was used for pair-wise comparison. ANOVA with repeated measures (for normally distributed data) or Friedman test (non-parametric ANOVA with repeated measures for non- normally distributed data) was used to compare more than two consecutive measures of numerical variables

followed by post hoc tests for pairwise comparisons of repeated readings. Due to multiple comparisons, the p-value was corrected using the Bonferroni method.

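### Cortisol, catecholamine, blood pressure and heart rate have a recorded baseline, but the group comparison does not use it and the repeated-measures step names no group term

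*Combined protocol and SAP*

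**What the plan says.** Two baselines are taken before any block. Under Preoperative, a cannula is placed 30 minutes before surgery "to collect 5 ml venous blood as preoperative sample for estimation of the level of cortisol and catecholamine". Under Induction and maintenance, during preoxygenation, "patients baseline hemodynamic parameters will be recorded regarding blood pressure, heart rate". Later readings follow: haemodynamics every 2.5 minutes, and hormone samples at 1 hour after the start and at 2 and 6 hours after the end of the procedure.

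The secondary outcomes include "Assessment of stress response with each technique through measuring cortisol and catecholamine levels" and "Hemodynamic Parameters regarding blood pressure and heart rate".

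The Statistical Methods section gives two relevant procedures for continuous data:

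- Between groups: "The comparisons between the three groups were done using either analysis of variance (ANOVA) for normally distributed quantitative variables", or Kruskal-Wallis when the data are not normal, then a post hoc pairwise test.
- Over time: "ANOVA with repeated measures (for normally distributed data) or Friedman test" "was used to compare more than two consecutive measures of numerical variables", "followed by post hoc tests for pairwise comparisons of repeated readings".

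A Bonferroni correction is stated. Chi-square and Fisher's exact tests are reserved for qualitative variables. The log-rank test and Cox regression are reserved for time to first analgesia request. The plan names no ANCOVA, change score, mixed model or baseline covariate.

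**The concern.** The trial collects a pre-treatment value for each of these four measures and then, as written, leaves it out of the comparison that answers the trial's question. A patient's follow-up cortisol or blood pressure usually depends in part on where that patient started. Ignoring the starting value leaves that between-patient variation in the error term, and with 25 per arm there is little precision to spare.

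The second procedure does not fill the gap. It is described as comparing consecutive readings, and its post hoc tests are between readings. Friedman's test has no between-group factor. Repeated-measures ANOVA can carry one, but the plan does not name it. A fall or rise over time within an arm says nothing about which technique changes the stress response, and a reader could mistake it for that.

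**Working it through.** **The plan's own figure.** The only calculated size is 23 per group for the pain score, by one-way ANOVA with 80% power at α = 0.05. It reproduces if the three means are spaced one unit apart (0, 1, 2) and the largest cited SD, 2.1, is used:

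- f = √(2/3) / 2.1 = 0.389
- noncentrality = 69 × 0.389² = 10.4
- power = 0.814

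Raising 23 to 25 allows for 8% drop-out. This calculation concerns pain only. The visual analogue scale is explained before surgery but no pre-operative score is recorded, so nothing below changes it.

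**Inputs for the four secondary measures.** There are 25 per arm, 75 in total, in three arms (Study Design and Statistical Methods). Tests are two-sided at 0.05, and 80% power is carried over from the sample size paragraph. The correlation ρ between baseline and follow-up is not in the documents. I assume 0.3, 0.5 and 0.7, and also show lower values.

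**Formulas, in units of the follow-up SD, for approximately normal data.**

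- Variance of an adjusted group difference relative to unadjusted: 1 − ρ².
- Cost of estimating the slope: a factor of 1 + 1/(75 − 3 − 2) = 1 + 1/70 = 1.014.
- Equivalent n per arm: 25 divided by the variance factor.
- Detectable difference between two arms, unadjusted: (1.960 + 0.842) × √(2/25) = 0.79 SD. Adjusted: multiply by √(1 − ρ²).

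| Assumed ρ | 1 − ρ² | With slope cost | Equivalent n per arm (with slope cost) | Detectable difference, SD (before slope cost) |
|---|---|---|---|---|
| 0.3 | 0.91 | 0.92 | 27.1 | 0.76 |
| 0.5 | 0.75 | 0.76 | 32.9 | 0.69 |
| 0.7 | 0.51 | 0.52 | 48.3 | 0.57 |

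Without the slope cost the equivalent n is 27.5, 33.3 and 49.0. Simulating 20,000 trials of 3 × 25 normal observations agrees with the table to within simulation error.

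**Low correlations.** With the slope cost, the variance factor is 1.01 at ρ = 0, 1.00 at 0.1 and 0.97 at 0.2.

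**In terms of power.** For an effect that the unadjusted three-group ANOVA detects with 80% power (f = 0.366), the adjusted analysis has power 0.838, 0.904 and 0.980 at ρ = 0.3, 0.5 and 0.7.

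**Chance imbalance.** The 95% limit for a baseline difference between two arms is 1.96 × √(2/25) = 0.55 SD. Unadjusted, it carries into the follow-up difference as ρ times its size, which is 0.17, 0.28 and 0.39 SD. This is the same precision loss seen another way, not an addition to it.

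**Change scores.** Comparing changes has variance 2(1 − ρ) relative to raw values: 1.4, 1.0 and 0.6. Adjustment gives 0.91, 0.75 and 0.51, so it does better at each value. Which of the two unadjusted forms the plan intends matters, and it does not say.

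**If repeated-measures ANOVA did carry a group factor.** Take three follow-up readings, equal correlation 0.5 between all readings, and a constant effect after baseline. Relative information (squared effect over variance) is then:

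- group main effect with baseline counted as one more reading: 0.75² / [(1 + 3 × 0.5)/4] = 0.90
- mean of the follow-ups, no baseline: 1 / [(1 + 2 × 0.5)/3] = 1.50
- the same mean adjusted for baseline: 1 / (0.667 − 0.25) = 2.40

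Treating the baseline as one more outcome reading is therefore worse than ignoring it, and much worse than using it as a covariate.

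**The case against.** The strongest reply is that the planned test is sound. Randomisation makes the unadjusted comparison valid, the plan adds pairwise tests and Bonferroni correction, and only secondary outcomes are involved. All of that stands, and it is why this is an improvement to a valid analysis rather than the repair of a biased one.

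The size of the gain is also unknown. Low correlations are plausible: the haemodynamic baseline is taken awake, and later readings are under anaesthesia with rises and falls actively treated. Hormone follow-up comes after surgical stress. Nothing in the documents supports 0.7 in particular. This limits the claim but does not remove it, because where the correlation is near zero adjustment costs only about 1.4% of variance.

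The detectable differences are not the trial's actual sensitivity. With Bonferroni over three pairwise comparisons, the unadjusted 0.79 SD becomes about 0.92 SD, and the adjusted values about 0.87, 0.79 and 0.65 SD. With 23 completers per arm and t-tests, the unadjusted figure is about 0.99 SD. The relative gain does not change. The figures also assume normal data and do not transfer directly to Kruskal-Wallis.

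Finally, repeated-measures ANOVA may have been meant to include group, and the plan nowhere says that tests over time will be read as group comparisons. That is fair, and the misreading is a risk rather than a stated intention. Still, a plan should name the term that answers its question, and the Friedman alternative cannot hold one.

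**Conclusion.** The concern holds. The documents record pre-block baselines for all four measures, compare groups on them without a baseline term, and describe the repeated-measures step only as a comparison over time. The consequence is lost precision, not bias. If the correlation is 0.3, 0.5 or 0.7, the avoidable part of the variance is 9%, 25% or 51% before the 1.4% slope cost. It is small at 0.3 and absent near zero. These figures rest on an assumed correlation, approximately normal data (possibly after transformation) and 25 patients per arm. The primary pain outcome and its sample size are untouched. The change should be made, because the data are already collected and the downside is negligible.

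**What to change.** For cortisol, catecholamine, blood pressure and heart rate, make the between-group analysis a baseline-adjusted model of the post-baseline values. This can be ANCOVA at each named time, or a mixed model with group, time, group-by-time and the baseline as covariate. Transform hormone levels only if they are skewed. Report between-group differences with 95% confidence intervals at each post-baseline time. State that within-group tests over time, including Friedman, are not used as evidence of a difference between techniques.

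Two related details need settling so that the model is defined:

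- Pre-specify which of the 2.5-minute haemodynamic readings, or which summary of them, is analysed. Fentanyl given for rises in heart rate or arterial pressure may blunt group differences, so report these results beside the total fentanyl dose already recorded.
- Reconcile the Sampling section, which announces three blood samples and then lists four times (before surgery, 1 hour after the start, and 2 and 6 hours after the end).

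The cost is analysis wording and a model in the SPSS package already named, with no new data or patients. ANCOVA at a single time spends one degree of freedom on the baseline. A mixed model also needs a stated covariance structure and, if the correlation with baseline may change over time, a baseline-by-time term.

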Comparison Between Ultra Sound Guided Rectus Sheath Block and Field Block for Midline Hernia Repair

NCT03225313

Start Date 20th August 2017

Investigators:

1. [name]

a. Other Investigators	[name]. [name].
	[name] [name]. [name] [name]. [name] [name]. [name]
c. Department name	Anesthesia Department.

Background and Rationale:

Pain is a complex but an important protective phenomenon. It may be defined as an unpleasant sensory and emotional experience associated with actual or potential tissue damage or described in terms of such damage (1). Good operative analgesia reduces the stress response to surgery, which is very important for patients with compromised cardiovascular respiratory functions (1). Good postoperative pain relief is important as it alleviates patient's distress and helps in rapid uncomplicated recovery (1).

Field block achieved by wound infiltration is a method of postoperative analysis commonly used alone or as a part of multimodal analysis regimens (2). It was developed to improve postoperative analysis, reduce opioid consumption and

hasten patient recovery .The use of local anesthetics (LAs) instead of opioid minimizes opioid adverse reactions, reduces nursing work, decreases resting pain, pain on motion, and thus allows better patient mobility (2). Field block carries the risk of wound infection and some surgeons oppose its use.

A rectus sheath block can provide effective pain relief for umbilical or other midline surgical incisions by blocking the intercostals nerves. It can be done using the landmark technique but it carries the risk of puncturing the posterior rectus sheath, peritoneum and bowel (3).

Use of ultrasound technology for rectus sheath block has reduced this risk considerably (3). Ultrasound guidance for regional anesthesia is associated with higher block success rates, shorter onset times, and reduced total anesthetic dose required and reduced complications. There is also the advantage of direct observation of pattern of anesthetic spread (4).

Objectives:

To compare between Ultra-sound guided rectus sheath block VS Field block infiltration in providing a good analgesia for patients undergoing midline hernia repair to detect which one is superior.

Study Design:

Prospective randomized double blinded controlled clinical trial will be done with a total number of 75 patients will be divided into 3 groups.

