The time to first analgesia request analysis was done using the Kaplan-Meier method and comparison between groups was done using the log-rank test. The Coxregression method was used to calculate the hazard ratio (HR) for risk estimation with its 95% confidence interval (CI). All tests were two-tailed. A p-value < 0.05 was considered significant.

Source of funding:

Will be provided by Theodor Bilharz Research Institute.

Time plan:

Starting date: August 2017.

References:

- 1. Merskey H. Classification of chronic pain: description of chronic pain syndromes and definitions of pain terms. Monograph for the subcommittee on Taxonomy International Association for the study of pam. Pain Suppl Vol 3. Amsterdam: Elsevier Science 1986.
- 4. Sites BD and Brull R. Ultrasound guidance in peripheral regional anesthesia: philosophy, evidence-based medicine, and techniques. Current Opinion in

Anesthesiology; 19: 630-9. 2006.

- 5. Paul F. White. New Criteria for Fast-Tracking After Outpatient Anesthesia: A Comparison with the Modified Aldrete's Scoring System. Anesth Analgesia criteria for fast tracking;88:1069–72. 1999.
- 6. Charlton S GJ. Cochrane Database of Systematic Reviews Perioperative transversus abdominis plane (TAP) blocks for analgesia after abdominal surgery (Review) Perioperative transversus abdominis plane (TAP) blocks for analgesia after abdominal surgery (Review). Cochrane Database Syst Rev Art. 2010;(12):1–59.
- 7. Flack SH, Martin LD, Walker BJ et al. Flack abstract. Available from: http://www2.pedsanesthesia.org/meetings/2011winter/syllabus/submissions/abstract s/wapd/GA30.pdf.

Research Template 12 Final Version: 14/11/2011

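### Bonferroni on the three between-group comparisons is valid but stricter than needed; Holm with pair-specific variances gives the same control and more power

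*Combined protocol and SAP*

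**What the plan says.** Under STATISTICAL METHODS, the three groups are compared by one-way ANOVA or, for non-normal data, Kruskal-Wallis, "then post-hoc test" for the pairs. The next sentence deals with repeated readings (repeated-measures ANOVA or Friedman, again with pairwise follow-up). A single general sentence then closes the paragraph: "Due to multiple comparisons, the p-value was corrected using the Bonferroni method". The section ends with "All tests were two-tailed" and "A p-value < 0.05 was considered significant".

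The post-hoc test is not named. The divisor is not given, and neither is the family to which the correction applies. The plan does not say that pairwise tests run only after a significant overall test.

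The Objectives section sets RSB against field block "to detect which one is superior". The sample size paragraph gives the planning values: the pain score "in RSB group was 4.65 ± 2.1", "in local infiltration group it was 5.45 ± 1.9" and "in control group it was 7.1 ± 1.1".

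**The concern.** Bonferroni holds every pair to the same strict level, even after other pairs have been rejected. With three groups that is more than family-wise control at 5% requires. The cost falls mainly on the comparison with the smallest planned difference. That is RSB versus field block, 5.45 − 4.65 = 0.80, which is the comparison named in the objective. The 23 per group was computed for the overall ANOVA at 0.05, so the stricter pairwise level was never allowed for in the sample size.

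**Working it through.** **Inputs.** Means 4.65, 5.45 and 7.1; SDs 2.1, 1.9 and 1.1; 23 evaluable per group (25 recruited); two-sided 0.05. All are from STATISTICAL METHODS. Assumption: three pairs, so Bonferroni uses 0.05/3 = 0.0167.

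**The plan's own figure.** For a three-group ANOVA, power follows from the noncentral F with λ = n·Σ(μᵢ − μ̄)²/σ². Means one unit apart in sequence (0, 1, 2) with SD 2.1 give λ = 23 × 2/4.41 = 10.43 and power 81.4%. With 22 per group, power is 79.5%. So 23 is reproduced, as a sample size for the overall test.

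**RSB versus field block, single test.** SD = √((2.1² + 1.9²)/2) = 2.00. Standard error = 2.00 × √(2/23) = 0.590. Ratio = 0.80/0.590 = 1.355.

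- At 0.05: Φ(1.355 − 1.960) = 27.3% (noncentral t: 26.3%).
- At 0.0167: Φ(1.355 − 2.394) = 14.9% (noncentral t: 14.0%).

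**Why the full division is not needed.** Holm tests the smallest p-value at 0.05/3, the next at 0.05/2 and the last at 0.05. It rejects everything Bonferroni rejects, and sometimes more, with the same family-wise guarantee. Here both comparisons with control are usually rejected first, so RSB versus field block is usually tested at 0.05. Closed testing gets there another way. If all three groups are equal, the 5% overall test controls the error; if exactly one pair is equal, only one true null exists and it is tested at 5%.

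**Simulation** (100,000 trials per scenario, 23 per group, planned means and SDs):

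| Procedure | RSB v field block | Field block v control |
|---|---|---|
| Welch pairs, Bonferroni | 14% | 85% |
| Welch pairs, Holm | 25% | 91% |
| Welch pairs, closed after Welch ANOVA | 26% | 94% |
| Pooled ANOVA error, Bonferroni | 22% | 79% |

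For a one-unit RSB versus field block difference, the Welch figures are 22%, 36.5% and 38%. With 25 per group and the 0.80 difference they are about 15%, 27% and 28%.

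**Error rates with the planned SDs, 23 per group.** Closed Welch testing has family-wise error of about 5% when all three groups are equal, when only the two blocks are equal, and when only field block and control are equal.

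The pooled error term is too small for RSB versus field block, because control's SD of 1.1 pulls it down: √((2.1² + 1.9² + 1.1²)/3) = 1.754 against 2.00. When the two blocks are truly equal, the pooled test of that pair rejects 8.6% of the time unadjusted after the overall test, and about 3.6% with Bonferroni. With Holm it rejects about 6.6% when the control difference is near 1.65 units, rising to 8.5% when control lies farther away.

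**The case against.** The strongest reply is that the 14% baseline is not shown to be the plan's. The plan names ordinary ANOVA and no Welch test. If the post-hoc test uses the ANOVA error term, the starting point is 22%, and moving to Welch with Holm or closed testing adds 25.0 − 22.2 = 2.8 to 26.5 − 22.2 = 4.3 points. This stands, and it limits the size of the claim. The gain for field block versus control is larger on that reading, from 79% to between 91% and 94%.

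A reader might infer that dividing by three protects against nothing. The documents do not support that. On the pooled reading, Bonferroni is what holds the RSB versus field block error below 5%. The gate that closed testing needs is also not written in the plan.

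A reader might also infer that the Bonferroni sentence can simply be deleted. It cannot: it is the plan's only multiplicity control, and it also covers the pairwise tests of repeated readings. Pain is scored at several times and none is named as primary. Suppose four independent times, with the blocks equal and the pair tested at each. At 0.05, the chance of at least one false claim is 1 − 0.95⁴ = 18.5%; at 0.0167 it is 1 − 0.9833⁴ = 6.5%. Positive correlation lowers both, but the protection is real.

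It is also fair to say that Bonferroni is a valid choice. This is a point of efficiency, not an error.

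**Conclusion.** The point holds for the three between-group comparisons at one outcome and one time. Bonferroni there is valid but stricter than necessary, and Holm is at least as powerful with the same control. The gain for RSB versus field block is about 11 points (14% to 25%) if the pairwise tests already use pair-specific variances, and 3 to 4 points if they use the pooled ANOVA error. It rests on a divisor of three and on the planned means and SDs; the closed-testing figures also need a significant Welch ANOVA first.

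A reader might infer that changing the correction makes the main comparison adequately powered. It does not: power stays near 25% to 28% for the planned 0.80 difference. By the normal approximation, 80% power would need 2 × (1.960 + 0.842)² × 2.00²/0.80², about 99 per group at 0.05. Sizing the trial on the overall test is the larger weakness.

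**What to change.** Replace the general sentence with two rules.

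1. *Between-group comparisons: the three pairs are compared by Welch t tests with Holm-adjusted p-values. Where Kruskal-Wallis is used, the three pairs are compared by rank tests with Holm-adjusted p-values.*
2. *Pairwise tests of repeated readings keep the Bonferroni correction, with the number of tests stated.*

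Closed testing is an acceptable alternative to the Welch part of rule 1: Welch ANOVA at 5% and, only if it is significant, each Welch pair at 5%. Do not relax the correction on tests that use the pooled variance, and do not relax control across the pain time points.

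The change needs no extra patients and only a few lines of text, and it should be fixed before group allocation is revealed to the analyst. The downside is that Holm and closed testing have no simple matching simultaneous confidence intervals, so pairwise 95% intervals should be labelled as individual ones.
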